9.7.3 Demographics and Other Baseline Characteristics

Demographic parameters (eg, age, race, ethnicity, sex, weight) and other baseline characteristics will be summarized by treatment group for the Safety and ITT Populations.

[REDACTED]

[figure not shown]
[REDACTED]

[REDACTED]

[REDACTED]

[REDACTED]

[REDACTED]

9.7.5 Efficacy Analyses

Efficacy analyses will be based on the ITT Population.

Baseline values for efficacy parameters will be derived from the eDiary in the Pretreatment Period, specifically the period of time from 14 days before randomization up to the time of randomization. The baseline weekly SBM or CSBM rate will be derived based on the total number of SBMs or CSBMs a patient had during this period. Baseline stool consistency and straining based on combined morning and evening assessments will be calculated as the observed weighted average of the nonmissing daily values during this period; the nonmissing daily value will be the average of nonmissing morning and/or evening assessments associated with the corresponding (ie, morning and/or evening) SBMs by the patient on that specific day. [REDACTED]

The sum of the weights during this period will be used in the denominator to calculate the observed weighted average of the nonmissing daily values.

Baseline abdominal pain or bloating daytime symptoms based on evening assessment will be calculated as the average of the nonmissing patient scores reported in the evening assessment.

Since the BM-related assessments and abdominal-symptom assessments in this study will be assessed twice daily via eDiary entries for efficacy parameters that will be derived based on the combined morning and evening assessments; a patient's daily score (based on combined morning and evening assessments) will be defined as the daily average (of the morning score and the evening score), except SBM and CSBM frequency. In case only the morning assessment score or only the evening assessment score is available, the available morning (or the available evening) assessment score will be taken as the patient's daily score.

[figure not shown]
An observed-cases approach to missing postbaseline data will be applied. The overall analysis (incorporating both age groups) including placebo and linaclotide doses (A, B, and C) will be the analysis to evaluate the main objective of this study. [REDACTED]

All statistical tests will be 2-sided hypothesis tests performed at the 5% level of significance. All confidence intervals (CIs) will be 2-sided 95% CI, unless stated otherwise. No multiplicity adjustment will be applied in this dose-ranging study. Nominal p-values will be provided for the efficacy parameters as a measure of strength of association between the endpoint and the treatment effect.

9.7.5.1 Primary Efficacy Parameter

The primary efficacy parameter is the change from baseline in 4-week overall SBM frequency rate (SBMs/week) during the Treatment Period. The numerator of the SBM rate (SBMs/week) during the Treatment Period will be derived based on the total number of SBMs a patient reported during this period in the morning and evening eDiaries.

For the primary efficacy parameter, comparison between each linaclotide dose (A, B, and C) and placebo will be performed using an analysis of covariance (ANCOVA) model with treatment and age group (7 - 11 years of age and 12 - 17 years of age) as factors and baseline value as a covariate.

9.7.5.2 *Secondary Efficacy Parameters*

Key Secondary Efficacy Parameter

The key secondary efficacy parameter is change from baseline in 4-week abdominal pain daytime symptoms based on evening assessment of abdominal pain symptoms.

Abdominal pain scores will be collected twice daily in the eDiary: in the morning when a patient wakes up and in the evening at bedtime. Patients are asked to rate their abdominal pain from the time the patient wakes up until bedtime as part of the evening assessment, and a 5-point rating scale is derived from the patient's responses. The patient's 4-week abdominal pain daytime symptoms during the Treatment Period are defined as the average of the nonmissing daily abdominal pain daytime symptoms reported in evening assessments in the eDiary during the 4-week Treatment Period.

Other Secondary Efficacy Parameters

Four change from baseline parameters are additional secondary efficacy parameters in this study. Their description and analyses are provided below.

Change From Baseline in 4-Week Stool Consistency

Stool consistency will be collected twice daily in the eDiary, in the morning when a patient wakes up and in the evening at bedtime, and measured using the 7-point p-BSFS. The patient's p-BSFS score in the 4-week Treatment Period will be the observed weighted average of the daily p-BSFS scores (using weight of 1 for full day and 0.5 for half day) and the denominator in the observed weighted average will be the sum of the weights during this period. The daily p-BSFS score will be the average of nonmissing morning and/or evening assessments of the p-BSFS score from the SBMs reported by the patient on that specific day during the Treatment Period.

Change From Baseline in 4-Week of Severity of Straining

Straining with each BM will be collected twice daily in the eDiary, in the morning when a patient wakes up and in the evening at bedtime, and measured using a 5-point scale. The patient's straining score in the 4-week Treatment Period will be the observed weighted average of daily straining score (using weight of 1 for full day and 0.5 for half day) and the denominator in the observed weighted average will be the sum of the weights during this period. The daily score for the Treatment Period will be the average of the nonmissing morning and/or evening assessments of the straining score from the SBMs reported by the patient on that specific day during the Treatment Period.

Change From Baseline in 4-Week Abdominal Bloating Daytime Symptoms Based on Evening Assessment

Abdominal bloating will be collected twice daily in the eDiary, in the morning when a patient wakes up and in the evening at bedtime. Patients are asked to rate their abdominal bloating from the time the patient wakes up until bedtime as part of the evening assessment, and a 5-point rating scale is derived from the patient's responses. The patient's 4-week abdominal bloating daytime symptoms during the Treatment Period are defined as the average of the nonmissing daily abdominal bloating daytime symptoms reported in evening assessments in the eDiary during the 4-week Treatment Period.

[figure not shown]
Change From Baseline in 4-Week Overall CSBM Frequency Rate (CSBMs/week) During the Treatment Period

[figure not shown]
A patient's 4-week overall CSBM frequency rate will be the CSBM rate (CSBMs/week) calculated over the 4-week Treatment Period. The numerator of the CSBM rate (CSBMs/week) during the 4-week Treatment Period will be derived based on the total number of CSBMs a patient reported during this period in his/her morning and evening eDiary.

[figure not shown]
Analysis Method for Change-From-Baseline Parameters

[figure not shown]
For each change-from-baseline parameter, each linaclotide dose group (A, B, and C) will be compared with the placebo group using an ANCOVA model with treatment (linaclotide doses A, B, and C, and placebo) and age group (7 - 11 years of age and 12 - 17 years of age) as factors and baseline value as a covariate.

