9.3 SELECTION OF STUDY POPULATION

9.3.1 Inclusion Criteria

To be eligible to participate in the study, patients must meet the following criteria:

1. Patient must provide written or verbal informed assent and the parent/guardian/LAR and caregiver must provide written informed consent before the initiation of any study-specific procedures (Section 5.3)
2. Patient is a male or female outpatient, weighing ≥ 18 kg, 7 to 17 years of age (inclusive) at the time the patient provides assent for the study and parent/guardian/LAR has provided signed consent

[figure not shown]

6. Patient meets Rome III criteria for child/adolescent IBS: at least once per week for at least 2 months before the Screening Visit, the patient experienced abdominal discomfort (an uncomfortable sensation not described as pain) or pain associated with 2 or more of the following at least 25% of the time:
 - a. Improvement with defecation
 - b. Onset associated with a change in frequency of stool
 - c. Onset associated with a change in form (appearance) of stool
7. Patient meets modified Rome III criteria for child/adolescent FC: For at least 2 months before the Screening Visit, the patient has had 2 or fewer defecations (with each defecation occurring in the absence of any laxative, suppository, or enema use during the preceding 24 hours) in the toilet per week

In addition, at least once per week, patient meets 1 or more of the following:

- a. History of retentive posturing or excessive volitional stool retention
- b. History of painful or hard bowel movements (BMs)
- c. Presence of a large fecal mass in the rectum
- d. History of large diameter stools that may obstruct the toilet
- e. *At least one episode of fecal incontinence per week*

8. Patient is willing to discontinue any laxatives used before the Pretreatment Visit in favor of the protocol-permitted rescue medicine ([Appendix III](#))

[figure not shown]
11. Patient has an average of fewer than 3 spontaneous BMs (SBMs) per week during the 14 days before the randomization day and up to the randomization (including the morning eDiary assessments reported before administration of first dose of double-blind investigational product on the randomization day). An SBM is defined as a BM that occurs in the absence of laxative, enema, or suppository use on the calendar day of the BM or the calendar day before the BM

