9.4 TREATMENTS

Patients meeting the eligibility criteria during Visit 3 (Day 1) will be randomized in a double-blind fashion to linaclotide or placebo ([Table 9.4.5-1](#)).

Randomization will be stratified by age group:

- Patients 7 to 11 years of age will be randomized to linaclotide doses (A, B, or C) or placebo in a 1:1:1:1 allocation
- Patients 12 to 17 years of age will be randomized to linaclotide doses (A, B, or C, or the approved adult dose, 290 ug) or placebo in a 1:1:1:1:1 allocation

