9.7.9 Determination of Sample Size

The planned sample size is designed for the overall analysis of placebo and linaclotide dose groups (A, B, and C), with 58 patients per treatment group (232 patients in total for the overall analysis). With the inclusion of additional 23 to 31 patients 12 to 17 years of age for the linaclotide approved adult dose, 290 ug, the planned sample size for the study is approximately 260 patients.

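### If linaclotide raises the SBM rate, the four-arm ANCOVA's single residual variance makes the Dose A and Dose B intervals too wide, despite equal arms

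*Protocol*

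**What the plan says.** The primary outcome is a change from baseline in SBMs per week over four weeks. It is built from a count: "The numerator of the SBM rate (SBMs/week) during the Treatment Period will be derived based on the total number of SBMs a patient reported" (Protocol 9.7.5.1). Each dose is compared with placebo "using an analysis of covariance (ANCOVA) model with treatment and age group" as factors and baseline as covariate (9.7.5.1). Section 9.7.5.2 uses the same model for the other change-from-baseline parameters, including the CSBM rate, and names the four treatment levels: "ANCOVA model with treatment (linaclotide doses A, B, and C, and placebo) and age group". The visible text says nothing about residual variance by arm or the type of standard error.

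The four arms are planned to be equal, "with 58 patients per treatment group (232 patients in total for the overall analysis" (9.7.9). Allocation among placebo, A, B and C is equal in both age strata (9.4). Section 9.7.5 sets two-sided 5% tests and 95% intervals, makes no multiplicity adjustment, and offers nominal p-values as a measure of strength of association. Entry is limited to low counts: "Patient has an average of fewer than 3 spontaneous BMs (SBMs) per week during the 14 days before the randomization day" (9.3.1).

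**The concern.** A count tends to spread as its mean rises. Entry holds baseline below 3 SBMs per week, while nothing caps the count on treatment. If the drug works, the higher-dose arms should therefore be more variable than placebo.

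Equal allocation is often taken as protection against unequal variances. It protects a two-arm comparison, where the pooled variance is the average of the two variances that matter. With four arms, the error term for Dose A against placebo also contains the scatter of Doses B and C, which has no place in that contrast.

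The objective is dose response (section 8.0). With no multiplicity adjustment, each dose is read from its own interval and nominal p-value. If the lower doses get intervals that are too wide, a real effect there is under-detected, which could tilt dose selection upward.

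**Working it through.** **Inputs from the protocol.** Four arms, 58 per arm, equal allocation, treatment and age group as factors, baseline as covariate, two-sided 5%. The plan's total reproduces: 4 × 58 = 232, and 232 + 23 to 31 = 255 to 263, which agrees with about 260. The visible text gives no effect, SD or power, so the 58 itself cannot be re-derived.

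**Formula.** Let vP, vA, vB and vC be the residual variances. With equal arms of size n, the correct squared standard error for dose X against placebo is (vP + vX)/n. The pooled model uses 2 × mean(vP, vA, vB, vC)/n. Hence

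ratio = pooled SE / correct SE = sqrt[2 × mean(vP, vA, vB, vC) / (vP + vX)]

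and coverage ≈ 2Φ(1.96 × ratio) − 1. With only two arms the ratio is 1.

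**Direction.** The ratio exceeds 1 when vP + vX is below the sum of the other two variances. If vP < vA < vB < vC:
- Dose A: vP + vA < vB + vC always, so too wide.
- Dose B: vP + vB < vA + vC always, so too wide.
- Dose C: too narrow only if vP + vC > vA + vB.

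**Size.** Assume overdispersed (gamma-Poisson) counts over four weeks, so that v = μ/4 + kμ², with μ in SBMs per week. All μ and k are assumptions.

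| Means P/A/B/C | k | A: ratio, coverage | B: ratio, coverage | C: ratio, coverage |
|---|---|---|---|---|
| Equal | any | 1.00, 95.0% | 1.00, 95.0% | 1.00, 95.0% |
| 2.5/2.8/3.1/3.5 | 1/3 | 1.11, 97.1% | 1.06, 96.2% | 0.99, 94.7% |
| 2/2.5/3/3.5 (linear) | 0.3 | 1.21, 98.2% | 1.09, 96.7% | 0.99, 94.7% |
| 2/3/3.4/3.5 (plateau) | 0.3 | 1.17, 97.8% | 1.08, 96.6% | 1.06, 96.2% |
| 2.5/3/3.5/4.5 (convex) | 1/3 | 1.22, 98.3% | 1.12, 97.2% | 0.95, 93.9% |
| 2/2/2.2/3.5 (mainly C) | 0.3 | 1.21, 98.2% | 1.16, 97.7% | 0.89, 92.0% |

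For the linear row, v = 1.70, 2.50, 3.45, 4.55, which sums to 12.20, so twice the mean is 6.10. Dose A: sqrt(6.10/4.20) = 1.205. Dose B: sqrt(6.10/5.15) = 1.088. Dose C: sqrt(6.10/6.25) = 0.988.

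**Power at Dose A, convex row.** Here v = 2.708, 3.750, 4.958, 7.875. The correct SE is sqrt((2.708 + 3.750)/58) = 0.334, and the pooled SE is 0.334 × 1.222 = 0.408. For the assumed difference of 0.5 SBMs per week:
- pooled: Φ((0.5 − 1.96 × 0.408)/0.334) = Φ(−0.90) ≈ 0.18
- correct: Φ((0.5 − 1.96 × 0.334)/0.334) = Φ(−0.46) ≈ 0.32

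**Simulation of the full ANCOVA** (58 per arm, age group and baseline in the model, 3,000 to 6,000 trials per scenario, k from 0.3 to 0.8). The results agree with the formula:
- Dose A standard error about 10 to 24% too large, coverage 97 to 99%. In the convex scenario (k = 1/3), power was 0.19 pooled against 0.31 with HC3.
- Dose B standard error about 4 to 14% too large under graded rises.
- Dose C coverage near 95% under linear means, about 96% under the plateau, 93 to 94% under the convex rise, and 91 to 92% when the effect is mainly at C.
- With equal means, pooled coverage was about 95%.
- Heteroscedasticity-consistent standard errors gave about 94 to 96% in every scenario. With equal means, HC3 widened the standard error by about 1%.

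**The case against.** **Rising variance is not documented.** The protocol gives no SD, no variance by arm and no expected effect. This stands, so the point is conditional. If no dose has an effect, the pooled intervals are correct and this mechanism does not inflate the global type I error.

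**Dose C.** A reader might infer that intervals err in opposite directions, too wide at Dose A and too narrow at Dose C. Rising variance alone does not give that. Dose C needs vP + vC > vA + vB, and nothing in the protocol says that the rise is concentrated at the top dose. Under linear means Dose C is about right, and under a plateau it is slightly wide.

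**Other endpoints.** It is tempting to extend the point to every parameter sharing the model. Pain, bloating, straining and stool consistency are averages of bounded scales, where the count argument does not apply; pain scores that improve move toward the floor and may spread less. Only the CSBM rate shares the count structure. No error in the linear-trend test has been shown either.

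**SAP detail.** The choice of standard error is often left to the SAP, which is not at hand and may already settle it, and parts of section 9.7.5 are redacted. The protocol contains no contradiction or wrong figure here. Even so, the model it names, in its ordinary form, gives miscalibrated intervals at the lower doses under the conditions the trial hopes to find.

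**Consequence.** This is a Phase 2 study with nominal p-values, and the error at the lower doses is conservative. Where the Dose A effect is small, power is low either way: with means 2.5/2.8/3.1/3.5 it was 0.07 to 0.10 pooled and 0.11 to 0.14 with HC3. That limits the stakes but does not remove them in a trial meant to locate the useful dose.

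**Conclusion.** The point holds in conditional form, for the SBM and CSBM rates only. If variance rises with the mean and the drug raises the mean across doses, the pooled ANCOVA gives intervals that are too wide at Dose A and, less so, at Dose B. The sizes in the working rest on assumed means and gamma-Poisson dispersion; the direction for A and B follows from the ordering of the variances alone. A much steeper or shallower dose response would move the figures. For Dose C no general direction can be claimed. This is an improvable analysis choice and worth changing, but not an error of fact in the protocol.

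**What to change.** Keep the ANCOVA with treatment, age group and baseline, and keep its point estimates. State that confidence intervals and p-values for the dose-placebo contrasts in SBM rate and CSBM rate will use heteroscedasticity-consistent (HC3) standard errors, or a model with arm-specific residual variances. Leave the bounded-scale endpoints as they are.

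The cost is one sentence in the analysis plan and one program option. If the variances turn out equal, the standard error is about 1% wider. If the SAP already specifies such an estimator, no change is needed beyond confirming that it covers both rates.

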9.7.6 Safety Analyses

The safety analysis will be performed using the Safety Population. The safety summaries will be provided by treatment group overall [REDACTED] [REDACTED]. The summaries of the linaclotide approved adult dose, 290 ug, will be included in the age group 12 to 17 years of age. The safety parameters will include AEs, [REDACTED]

9.7.6.1 Adverse Events

[figure not shown]
[figure not shown]
AEs will be coded using the *Medical Dictionary for Regulatory Activities* (MedDRA), Version 18.0 or newer.

An AE (classified by preferred term) that occurs during the Treatment Period will be considered a TEAE if it was not present before the date of the first dose of double-blind investigational product or was present before the date of the first dose of double-blind investigational product and increased in severity during the Treatment Period. If more than 1 AE is reported before the date of the first dose of double-blind investigational product and coded to the same preferred term, the AE with the greatest severity will be used as the benchmark for comparison with the AEs occurring during the Treatment Period that were also coded to that preferred term. An AE that occurs more than 1 day after the date of the last dose of double-blind investigational product will not be counted as a TEAE.

The number and percentage of patients reporting TEAEs in each treatment group will be tabulated by SOC and preferred term;

The incidence of common ($\geq 5\%$ of patients in any treatment group) TEAEs, on-therapy SAEs,

In addition, the incidence of fatal on-therapy SAEs (ie, events that caused death) will be summarized separately by treatment group and preferred term.

[REDACTED]

[REDACTED]

[REDACTED]

[REDACTED]

[REDACTED]

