9.0 INVESTIGATIONAL PLAN

9.1 OVERALL STUDY DESIGN AND PLAN: DESCRIPTION

This clinical study will be a multicenter, randomized, double-blind, placebo-controlled, parallel-group, safety and efficacy study comparing 1 of 3 linaclotide doses (A, B, and C) or 290 ug (only patients 12 - 17 years of age) with placebo in pediatric patients, 7 to 17 years of age, with a diagnosis of IBS-C based on Rome III child/adolescent criteria (ie, fulfill Rome III criteria for child/adolescent IBS and fulfill modified Rome III criteria for child/adolescent FC). The study will include a total of 6 visits and will be approximately 9 to 12 weeks in duration (Figure 9.1.4-1). Approximately 260 patients with IBS-C will be enrolled in this study.

- Screening Period (14 to 28 days)
- Pretreatment Period (14 to 21 days)
- Double-blind Treatment Period (hereinafter referred to as Treatment Period) (at least 28 days [4 weeks] on treatment)
- Post-treatment Period (at least 7 days [1 week] after the Week 4 End-of-Treatment Visit)

[figure not shown]

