9.3.2 Exclusion Criteria

Patients who meet any of the following criteria will not be eligible to participate in the study:

[figure not shown]
1. Patient reports having more than 1 loose, mushy stool (eDiary-recorded stool consistency of 6 on the Pediatric Bristol Stool Form Scale [p-BSFS]) or any watery stool (eDiary-recorded stool consistency of 7 on the p-BSFS) with any SBM that occurred in the absence of laxative use on the calendar day of the BM or the calendar day before the BM during the 14 days before the randomization day and up to the randomization

[figure not shown]

6. Patient has required manual disimpaction anytime prior to randomization or disimpaction during in-patient hospitalization within 1 year prior to randomization

16. Patient is unable to tolerate the placebo prior to randomization

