9.4.1 Treatments Administered

Investigational product in the form of liquid oral solution or solid oral capsules will be packaged in bottles and provided by the Sponsor. Patients will be supplied with blinded investigational product and will be instructed to take their assigned dose orally, once daily as a single dose.

[REDACTED]

[REDACTED]

9.4.1.1 *Rescue Medication*

During the Pretreatment and Treatment Periods, a patient may use dispensed, protocol-permitted laxatives as rescue medication.

[REDACTED]

Protocol-permitted rescue medication will be a choice of senna (oral) or bisacodyl (oral or rectal) that will be dispensed according to the [Schedule of Evaluations](#) (Section 2.0).

[REDACTED]

[REDACTED]

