9.5.2.1 Adverse Events

An AE is any untoward medical occurrence in a patient or clinical investigation patient administered a pharmaceutical product and which does not necessarily have to have a causal relationship with this treatment. An AE can therefore be any unfavorable and unintended sign (including an abnormal laboratory finding, for example), symptom, or disease temporally associated with the use of a medicinal product, whether or not considered related to the medicinal product (ICH-E2A).

For the purpose of the site's data collection responsibilities, any untoward event that was reported from the time written consent was obtained until 30 days after the final protocol-defined study visit (or the last known dose of investigational product if the final visit does not occur) is to be considered an AE.

Examples of AEs are as follows:

- Changes in the general condition of the patient
- Subjective symptoms offered by or elicited from the patient
- Objective signs observed by the Investigator or other study site personnel
- All diseases that occur after signing the informed consent, including any change in severity or frequency of preexisting disease
- All clinically relevant abnormalities in laboratory values or clinically relevant physical findings that occur during the study schedule

Please note medical procedures scheduled prior to consenting, but occurring during the study should not be captured as AEs, but should be listed in the medical history if related to a pre-existing condition.

[REDACTED]

[REDACTED]

[REDACTED]

[REDACTED]

[REDACTED]

[REDACTED]

9.5.2.2 *Causality Assessment*

For each AE, the Investigator must provide an assessment of causal relationship to the investigational product. The causality assessment must be recorded on the appropriate AE reporting page of the patient's eCRF. Causal relationship must be assessed by answering the following question:

Is there a reasonable possibility the investigational product caused the event?

Yes: **There is evidence to suggest a causal relationship between the investigational product and AE, ie:**

- There is a reasonable temporal relationship between the investigational product and the event, and/or
- The event is unlikely to be attributed to underlying/concurrent disease, other investigational products, or other factors, and/or
- Positive dechallenge and/or rechallenge exist

No: **There is no evidence to suggest a causal relationship between the investigational product and AE, ie:**

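### The TEAE severity benchmark is not limited to AEs ongoing at first dose, so a new on-treatment AE no worse than an earlier resolved one of the same term is not counted

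*Protocol*

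**What the plan says.** Protocol Section 9.7.6.1 gives two routes to a TEAE, both judged by preferred term. An AE in the Treatment Period "will be considered a TEAE if it was not present before the date of the first dose of double-blind investigational product", or if it "was present before the date of the first dose of double-blind investigational product and increased in severity during the Treatment Period". The benchmark for the second route follows: "If more than 1 AE is reported before the date of the first dose of double-blind investigational product" under one preferred term, "the AE with the greatest severity will be used as the benchmark for comparison with the AEs occurring during the Treatment Period".

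Four other places determine how far back this reaches and what it can catch:

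- Section 9.5.2.1 starts AE collection at consent: "any untoward event that was reported from the time written consent was obtained until 30 days after the final protocol-defined study visit".
- Section 9.1 gives Screening as 14 to 28 days and Pretreatment as 14 to 21 days. Section 9.1.1 agrees, placing the start of Screening up to 7 weeks before randomization.
- The rescue medication paragraph of Section 9.4.1 states: "During the Pretreatment and Treatment Periods, a patient may use dispensed, protocol-permitted laxatives as rescue medication". The products are senna and bisacodyl.
- Exclusion criterion 1 in Section 9.3.2 limits loose and watery stools only "with any SBM that occurred in the absence of laxative use on the calendar day of the BM" or the day before, and only in the 14 days before randomization.

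**The concern.** A treatment-emergent rule should separate symptoms the child already had at first dose from events that began afterwards. This rule compares severity with the worst earlier episode of the same term, whether or not that episode had ended. A child who had a short laxative-related diarrhea episode in the Pretreatment Period, recovered, was randomized, and then developed diarrhea of the same grade on linaclotide has a new event that the TEAE table omits.

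Diarrhea is the term where this matters most. Section 7.2 names it as the most common AE in the adult program. Section 7.2.1 reports post-marketing severe diarrhea needing hospitalization or intravenous fluids, and says this is the first placebo-controlled evaluation in pediatric IBS-C. Safety by dose is a study objective (Section 8.0), and Section 9.7.6.1 reports patients with TEAEs by preferred term. A child whose event is removed stays in the denominator, so the reported percentage falls.

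**Working it through.** The protocol states no figure for this point, so there is none to reproduce. The check has four steps.

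**1. Length of the pre-dose window.** Shortest: 14 + 14 = 28 days. Longest: 28 + 21 = 49 days. The Treatment Period is at least 28 days, so the look-back is about as long as treatment or longer.

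**2. Does the rule reach resolved events?** The text has no condition on whether the earlier AE is ongoing. The benchmark sentence provides for several pre-dose AEs of one term in one child. Separate AEs of the same term are normally separate episodes, so at least one has usually ended. The wider reading is therefore the natural one.

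**3. Which combinations count.** Section 9.5.2.3 has three severity grades.

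| Worst earlier episode | New mild | New moderate | New severe |
|---|---|---|---|
| Mild | not counted | TEAE | TEAE |
| Moderate | not counted | not counted | TEAE |
| Severe | not counted | not counted | not counted |

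Three of nine combinations count. If the benchmark applied only to ongoing AEs, a new episode after a resolved one would count in all nine.

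**4. Illustrative size.** Let p be the share of children with on-treatment diarrhea, f the share with a recorded pre-dose diarrhea AE, and g the share of later events no more severe than the earlier one. If earlier and later diarrhea are independent:

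- fraction of affected patients missed = f × g
- patients missed per arm = n × p × f × g, with n = 58 (Section 9.7.9)

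Neither f nor g is in the protocol. I assume f = 5% to 15% and g = 70% to 90%. For p, Section 7.2 gives about 20% in the two adult registration IBS-C studies and 9% to 12% in the two IBS-C studies outside North America. These are adult rates over 12 or 26 weeks, used only as a range.

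- f × g: 0.05 × 0.70 = 3.5% to 0.15 × 0.90 = 13.5%
- Lowest: 58 × 0.09 × 0.035 = 0.18 patients
- p = 12%, upper end: 58 × 0.12 × 0.135 = 0.94
- p = 20% (11.6 expected patients): 11.6 × 0.035 = 0.41 to 11.6 × 0.135 = 1.57

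The overall range is about 0.2 to 1.6 patients per arm. At p = 20% the reported rate would be 20% × (1 − 0.135) = 17.3% to 20% × (1 − 0.035) = 19.3%.

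If children with earlier diarrhea are more prone to it on drug, more is lost. With f = 10% and their risk twice the 20% average, they supply 0.10 × 0.40 / 0.20 = 20% of affected patients, so 20% × 0.70 to 0.90 = 14% to 18% are missed (1.6 to 2.1 of 11.6). If their risk is instead twice that of the other children, they supply 0.2 / (0.2 + 0.9) = 18.2%, and 12.7% to 16.4% are missed (1.5 to 1.9).

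**Effect on comparisons.** If f × g is the same in both arms, a true difference p₁ − p₀ is reported as (p₁ − p₀)(1 − f × g). The absolute difference shrinks by the same 3.5% to 13.5%, and the ratio is unchanged.

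**The case against.** The rule can be defended as a baseline adjustment applied alike in every arm. IBS-C symptoms fluctuate, rescue laxatives remain allowed on treatment, and a same-grade laxative-related episode is not clearly due to the drug. Abdominal pain or discomfort is an entry criterion, so counting every recurrence would add background events, placebo included. This stands as a real cost of the change. It does not justify letting an episode that ended weeks earlier cancel a new one; attribution is better left to the comparison with placebo.

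The pathway is also narrow. The earlier diarrhea must have been recorded as an AE and coded to the same preferred term, in a child selected for few bowel movements, and exclusion criterion 1 removes many children with laxative-free loose stools. A severe pre-dose episode in a child who is then randomized should be rare. This limits the size of the effect, and the inputs f and g remain assumptions.

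Three stronger readings are tempting, and the protocol does not support them:

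- A reader might infer that any diarrhea on treatment is lost once a child had diarrhea before. It is counted whenever it is more severe than the worst earlier episode.
- A reader might infer a bias in favor of one arm. The rule is the same in all arms and dilutes a difference without producing one.
- A reader might infer that serious or hospitalized cases disappear. Section 9.7.6.1 names on-therapy SAEs as a separate output, and Section 9.5.2.5 requires every AE to be entered in the eCRF.

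Finally, the word for an AE being present before first dose could mean ongoing at first dose. The benchmark sentence, which refers to AEs reported before that date, points the other way. Parts of Sections 9.5.2.1 and 9.7.6.1 are redacted and the SAP is not shown. Either may add diarrhea summaries, but that would not change the definition that is visible.

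**Conclusion.** The point holds in a limited form. As written, a new on-treatment AE that is no more severe than a resolved, recorded AE of the same preferred term in the 28 to 49 days before first dose is not a TEAE. This biases TEAE incidence downward in all arms and pulls absolute differences from placebo toward zero. It concerns diarrhea above all, and abdominal pain by the same mechanism.

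The size is probably small: about 0.2 to 1.6 patients per 58-patient arm under independence, and about 1.5 to 2.1 in the illustrated case of higher risk in prone children at the 20% rate. Every such figure rests on the assumed f and g and on adult diarrhea rates. The change is a cheap improvement to the main known safety signal; it does not correct an error that would overturn the trial's safety conclusions.

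**What to change.** Reword Section 9.7.6.1 so that:

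- an AE with onset on or after the first dose of double-blind product, within the existing end of the TEAE window, is a TEAE even if an AE of the same preferred term had resolved before first dose;
- the worst-severity benchmark applies only to AEs still ongoing at first dose, which become TEAEs if they worsen during treatment.

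The cost is a sentence or two and a programming flag from AE start and stop dates, plus a stated rule for incomplete dates. No clinical procedure changes. The downside is that some background recurrences, such as abdominal pain or laxative-related diarrhea, will be counted in every arm, placebo included, and the definition may differ from the adult program's. Keeping the present definition as a supplementary table preserves comparability and shows how many patients the choice affects.
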